3.2. Study Design

This is an open-label, multicenter, sequential dose-escalation study to evaluate the safety, tolerability, PK, and PD of GS-5829 as a single agent in subjects with advanced solid tumors and lymphomas and in combination with exemestane or fulvestrant in subjects with advanced estrogen receptor positive breast cancer.

Group 1: Single agent GS-5829 in solid tumors and lymphomas

Cohorts of subjects with advanced solid tumors and lymphomas who have failed or are intolerant to standard therapy or for whom no standard therapy exists will be sequentially enrolled at progressively higher dose levels to receive oral GS-5829 as monotherapy once daily (QD). The starting dose will be 0.6 mg. Each dose level will enroll 1 subject until a \geq Grade 2 treatment-related toxicity is observed within the initial dosing period (Study Day 1 through C1D28 for all cohorts). At Dose Level 5 or if a \geq Grade 2 treatment-related toxicity is observed (whichever occurs first), the dose level will be expanded to 3 subjects. (Note: subjects enrolled with a Grade 2 hemoglobin [Hb] must have Hb worsen by at least 1 grade from baseline to be considered for expansion of the cohort to 3 subjects). Once a dosing level has been expanded to 3 subjects, a standard 3+3 study design will begin and, dose escalation [3+3] will be performed with cohort sizes of 3 to 6 subjects. Subjects in the first 3 cohorts will receive a single dose and then approximately 7 days later, initiate dosing once daily. Subjects will return to the clinic for frequent evaluation and monitoring as per [Appendix 2](#).

The doses for each candidate dose level in Group 1 are shown in [Table 3-1](#).

Table 3-1. Group 1: Single Agent GS-5829

Dose Level	GS-5829*
1	0.6 mg
2	1.4 mg
3	2 mg
4	3 mg
5	4 mg
6	6 mg
7	9 mg
8	12 mg

* Dose levels may be modified based on emerging safety and PK results.

If a DLT occurs within the 28 day DLT period at any dose level, this level will be expanded to enroll 3 additional subjects.

The safety and tolerability of each dose level will be assessed by a safety review team (SRT) after all subjects in the cohort have been followed for at least 28 days after the first dose of GS-5829. If no DLTs occur in up to 3 subjects or < 2 DLTs occur in up to 6 subjects on any Dose Level after 28 days on treatment, the next Dose Level will open. Each subsequent Dose Level will open if the Dose Level preceding has no DLTs in 3 subjects or < 2 DLTs in up to 6 subjects.

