-1	is ≥25% less total GS-5829 administered over a 28 day period	6 subjects	If no DLT in 6 subjects at this dose level, then expand to maximum total of all Group 3 subjects of 40 (approx. 28 additional subjects)

Sites in France will be limited to Group 3 enrollment only.

Dose escalation in Group 1 will continue until identification of the MTD, or a suitable lower recommended dose, for Phase II studies. At least 6 subjects should be treated and evaluated at the GS-5829 dose level recommended for Phase II studies.

A DLT in Group 1 or 2 is a toxicity defined below considered possibly related to GS-5829 occurring during the DLT assessment window (Study Day 1 through C1D28) in each cohort.

- Grade ≥ 4 neutropenia (absolute neutrophil count [ANC] < 500/mm³)
- Grade ≥ 3 neutropenia (ANC < 1000/mm³) with fever (a single temperature of > 38.3°C or a sustained temperature of ≥ 38°C for more than one hour)
- Grade ≥ 3 thrombocytopenia
- Grade ≥ 2 bleeding (e.g. gastrointestinal, respiratory, epistaxis, purpura)
- Grade ≥ 3 or higher non-hematologic toxicity, except:
 - Grade 3 nausea or emesis with maximum duration of 48 hours on adequate medical therapy
 - Grade 3 diarrhea which persists for < 72 hours in the absence of maximal medical therapy
- Grade ≥ 2 non-hematologic treatment-emergent adverse event (TEAE) that in the opinion of the investigator is of potential clinical significance such that further dose escalation would expose subjects to unacceptable risk
- Treatment interruption of ≥ 7 days due to unresolved toxicity
- For certain toxicities such as laboratory assessments without a clear clinical correlate, a discussion between the Investigator and Medical Monitor may take place to determine if

this AE should be assessed as a DLT necessitating dose reduction. However, any Grade 3 or Grade 4 elevation in AST or ALT associated with a Grade 2 elevation in bilirubin that is at least possibly related to study drug will be considered a DLT.

Group 3: For the first 6 subjects enrolled in the aggressive lymphoma group (Group 3), a modification of the DLT assessment for hematologic toxicity will be:

- Grade ≥ 4 neutropenia (absolute neutrophil count [ANC] $< 500/\text{mm}^3$) which persist for > 3 days upon interruption of GS-5829 (administration of growth factors not allowed concurrently, but allowed during GS-5829 interruption)
- Grade ≥ 4 thrombocytopenia ($< 25,000/\text{mm}^3$)

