3.3. Study Treatments

Subjects who meet eligibility criteria will receive GS-5829 orally once daily. Subjects in the first 3 cohorts will receive a single dose of GS-5829 and then approximately 7 days later start their first 28 day cycle of GS-5829 once daily. Each cycle will consist of 28 days. Safety and efficacy assessments will occur on an outpatient basis including assessment of tumor response, physical exam, vitals, electrocardiogram (ECG), collection of blood samples (for routine safety labs, GS-5829 PK, CCI [REDACTED] at applicable visits), urine pregnancy (every 4 weeks while receiving GS-5829 in females of childbearing potential), and assessment of AEs. In addition, subjects will undergo computed tomography (CT)/magnetic resonance imaging (MRI) or applicable scans every 8 weeks for the first year and then every 12 weeks. Subjects in Group 3 will undergo a PET/CT if available instead of a CT scan alone at week 16.

A subject who does not show evidence of disease progression by clinical assessment or by CT/MRI or applicable scan may continue receiving GS-5829 once daily until disease progression (clinical or radiographic), unacceptable toxicity, withdrawal of consent, or other reasons specified in Section 3.4.

For subjects in Group 2, a radionuclide bone scan (whole body) is also required at screening and then as clinically indicated or to confirm a complete response.

Study drug dosing will continue in the absence of disease progression or toxicity warranting discontinuation of therapy.

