8.1.2. Primary Endpoint

The primary endpoint of this study is incidence of DLT as defined in Section 3.2.

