8.2.1.3. DLT-Evaluable Analysis Set

The DLT-Evaluable Analysis Set includes all subjects in the Safety Analysis Set who complete all treatment and safety procedures through Day 29, or experienced a DLT prior to Day 29. Determination of the MTD will be in DLT-Evaluable Analysis Set.

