Appendix 2. Study Procedures Table

Study Phase Cycle Day	Screening Day 28	Study Day 1 ^a	First 28 Days							Cycle 2 Day 1 and Every 2 weeks*	Cycle 2 Day 1 and Every 4 weeks	Every 8 weeks	EOT	30 day Safety Follow-up ^k
			Cycle 1 Day 1 ^b	Day 2	Day 4	Day 8	Day 11	Day 15	Day 22					
Window (day)	-28	±0	±3	±0	±0	±1	±1	±2	±3	±7	±7	±7	±7	±7
Informed Consent	X													
Medical and Medication History ^c	X													
Physical Examination ^d	X	X	X	X	X	X	X	X	X	X			X	
Vital Signs ^e	X	X	X	X	X	X	X	X	X	X			X	
Oxygen saturation ^f	X	X	X	X	X	X	X	X	X	X			X	
Echocardiogram ^f	X										X		X	
Triplicate 12-lead ECG ^g	X	X	X			X					X		X	
Adverse events/ Concomitant medications ^h	X	X	X	X	X	X	X	X	X	X			X	X
IP Dispensing		X ⁱ	X								X			
Exemestane or Fulvestrant ^w (Group 2 only)			X					X			X			
Dosing Diary Accountability			X	X	X	X	X	X	X	X				
IXRS Registration	X	X	X ⁱ							X			X	
CBC with differential	X ^s	X	X		X	X	X	X	X	X			X	
Chemistry ^y	X ^s	X	X		X	X	X	X	X	X			X	
Coagulation ^q	X ^s		X			X					X		X	
25-hydroxy vitamin D (Group 2 only)	X													
Urinalysis and Urine Chemistry		X	X			X			X	X			X	

[figure not shown]
Study Phase Cycle Day	Screening Day 28	Study Day 1 ^a	First 28 Days							Cycle 2 Day 1 and Every 2 weeks*	Cycle 2 Day 1 and Every 4 weeks	Every 8 weeks	EOT	30 day Safety Follow-up ^k
			Cycle 1 Day 1 ^b	Day 2	Day 4	Day 8	Day 11	Day 15	Day 22					
Window (day)	-28	±0	±3	±0	±0	±1	±1	±2	±3	±7	±7	±7	±7	±7
Pregnancy Test ^l	X	X	X ⁱ								X		X	
GS-5829 Intensive PK ^m		X	X			X					X ^v			
GS-5829 Sparse PK ^m					X			X			X ^v			
CCI														
CCI														
CCI														
Biopsies for Group 3 lymphoma expansion ^x	X									X ^x			X	
CT Scan w/Contrast or MRI ^p	X											X	X ^p	
PET Scan (Group 3 only) ^z	X													
Bone Scan(Group 2 only)	X												X	
ECOG Performance Status	X	X	X			X		X	X				X	
Treatment Response Assessment ^t												X	X	

* Day 1 of subsequent cycles.
 a Study Day 1 is applicable to Cohorts 1-3 only of Group 1.
 b Cycle 1 Day 1 occurs on Study Day 7 for subjects in Cohorts 1-3 of Group 1 and must occur at least 5 days, but no more than 9 days after Study Day 1. For Group 1 Cohorts 4 and higher and all cohorts of Group 2 the first day of study is Cycle 1 Day 1.
 c Medical history includes significant past medical events (eg, prior hospitalizations or surgeries), a review of the disease under study, prior anti-cancer therapies, and any concurrent medical illnesses.

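### No blood count or chemistry is required between Day 22 and the close of the DLT window, and the protocol's cut-offs disagree on whether an abnormality first found at Cycle 2 Day 1 is a DLT

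*Protocol*

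**What the plan says.** Protocol Section 8.1.2 states: "The primary endpoint of this study is incidence of DLT as defined in Section 3.2". For Groups 1 and 2, Section 3.2 limits a DLT to a possibly related toxicity "occurring during the DLT assessment window (Study Day 1 through C1D28) in each cohort". The criteria include "Grade ≥ 3 thrombocytopenia", Grade 4 neutropenia, and a Grade 3 or 4 transaminase rise accompanied by raised bilirubin. Each of these is established by a blood test.

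In Appendix 2 the row "CBC with differential" is marked in Cycle 1 on Days 1, 4, 8, 11, 15 and 22, and then in the column "Cycle 2 Day 1 and Every 2 weeks". The chemistry row has the same pattern. The visit window is ±3 days for Day 22 and ±7 days for the Cycle 2 column. Section 3.3 says "Each cycle will consist of 28 days", so Cycle 2 Day 1 (C2D1) is nominal Day 29. Section 6.1.13 allows Day 1 pre-dose samples to be taken up to two days before the visit.

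The cut-offs differ by section:

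- Section 3.2: the window includes C1D28. The same section also refers to a 28-day DLT period and defines the MTD on the first 28 days of dosing.
- Section 6.6: safety procedures through Day 28, or a DLT before Day 28.
- Section 8.2.1.3, the set in which the MTD is determined: subjects who "complete all treatment and safety procedures through Day 29, or experienced a DLT prior to Day 29".

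The safety review team (SRT) assesses a Group 1 dose level "after all subjects in the cohort have been followed for at least 28 days after the first dose of GS-5829". SAP Section 7.1.7.1 only lists DLTs. Neither document says how to date a laboratory DLT.

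**The concern.** A low platelet or neutrophil count may cause no symptoms. Its onset then cannot be placed before the sample that shows it. If it arises after the Day 22 draw and is first seen on Day 29, the plan does not say whether it occurred inside the window.

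The toxicity concerned is a central one. Protocol Section 1.5 names thrombocytopenia as the earliest sign of toxicity with another bromodomain inhibitor, and reports a Grade 3 thrombocytopenia DLT in this study at 3 mg. SAP Section 7.1.7.2 makes decreased platelets an adverse event of interest.

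DLT counts open each Group 1 dose level, define the MTD and feed the Group 2 dose-DLT model. A missed or late-dated event can move the count only downwards.

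**Working it through.** The plan states no operating characteristics for this point, so there is no figure to reproduce.

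**1. Calendar** (Appendix 2, C2D1 = Day 29)

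- Nominal visits: counts on Days 22 and 29. Days 23 to 28 have no scheduled count: 28 − 22 = 6 days, 6/28 = 21% of the window.
- Day 22 visit at its limits: on Day 25 the uncovered tail is 3 days (11%); on Day 19 it is 9 days (32%).
- C2D1 visit: 29 ± 7 gives Days 22 to 36, which is 15 permitted days. Seven (Days 22 to 28) are inside the window and eight are outside.
- Longest permitted gap between the two counts: 36 − 19 = 17 days.

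**2. A Grade 3 platelet count first seen on a given day, if the sample date is taken as onset (an assumption)**

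| Sample day | 3.2 (through C1D28) | 6.6 (before Day 28) | 8.2.1.3 (before Day 29) |
|---|---|---|---|
| 27 | DLT | DLT | DLT |
| 28 | DLT | not covered | DLT |
| 29 | not a DLT | not covered | not covered |

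On the last row, the subject has completed procedures through Day 29 and so can enter the MTD set as DLT-free.

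**3. Illustrative effect on escalation**

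Assumptions: true 28-day DLT rate p = 0.33, constant hazard, no early or unscheduled draw, and every laboratory-only DLT after the last count is lost.

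- Captured rate with the last count on day d, all DLTs laboratory-only: q = 1 − (1 − p)^(d/28). For d = 22, q = 1 − 0.67^(22/28) = 0.270.
- If half of DLTs are laboratory-only: q = 0.5 × 0.33 + 0.5 × 0.270 = 0.300.
- 3+3 escalation: (1 − q)³ + 3q(1 − q)² × (1 − q)³.
- P(≤1 DLT in 6): (1 − q)⁶ + 6q(1 − q)⁵.

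| Case | q | 3+3 escalates | P(≤1/6) |
|---|---|---|---|
| Full capture | 0.330 | 0.43 | 0.36 |
| Last count Day 25, all laboratory-only | 0.301 | 0.49 | 0.42 |
| Last count Day 22, half laboratory-only | 0.300 | 0.49 | 0.42 |
| Last count Day 22, all laboratory-only | 0.270 | 0.56 | 0.49 |
| Last count Day 19, all laboratory-only | 0.238 | 0.63 | 0.56 |

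With onset spread evenly over 28 days instead, Day 22 gives q = 0.33 × 22/28 = 0.259, and the probabilities are 0.58 and 0.51. The result depends little on that choice.

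**The case against.** The best defence is that Section 3.2 defines a DLT by when the toxicity occurs, not by when a scheduled sample finds it. Nothing in either document assigns the sample date as the onset date. An investigator could judge that a Grade 3 platelet count seen on Day 29 began on Day 27 and report a DLT. This stands against a stronger claim that a reader might infer from the calendar, namely that late laboratory DLTs fall outside the primary endpoint. The documents do not exclude them; they leave their classification open.

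Sampling inside the window is also possible. The C2D1 window opens on Day 22, a nominal visit may be sampled on Day 27 or 28, and Section 6.3.4 has unscheduled procedures recorded. So it would be wrong to say that the rate is observed only to about Day 22. But early draws are optional, and nothing prompts an unscheduled one in a subject without symptoms.

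Section 8.2.1.3 asks for procedures through Day 29, which on the nominal schedule brings C2D1 into the requirement. Section 3.2 has the SRT review all relevant available data, and its 28 days are a minimum. This narrows the gap without closing it. The same sentence of 8.2.1.3 counts a DLT only before Day 29, Section 6.6 asks only for Day 28, and no text makes the C2D1 result a condition of the SRT decision.

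On size, clinical DLTs are unaffected by the blood schedule. Of the two DLTs described in Section 1.5, one was an adrenal hemorrhage and one was thrombocytopenia. That is why the figures that treat every DLT as laboratory-only are upper bounds.

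**Conclusion.** The point holds as a gap in coverage combined with inconsistent cut-offs. At nominal visits 6 of 28 days (3 to 9 across the Day 22 window) have no required blood count or chemistry, and the next sample falls one day after the window closes. The same silent abnormality may or may not be counted, depending on booking and on which section is applied.

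With the last count on Day 22 and a true rate of 33%, the upper bound is a rise in 3+3 escalation from 0.43 to 0.56, and in P(≤1/6) from 0.36 to 0.49. With half of DLTs laboratory-only the values are about 0.49 and 0.42. These rest on an assumed rate, onset pattern and laboratory share; the documents give none of them.

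A reader might infer that escalation in this trial was too permissive, or that a toxicity building up with daily dosing would lose even more. Neither is shown. The documents contain no onset-time data, and calling thrombocytopenia the earliest sign of toxicity does not place it in Week 4. Only the direction of a missed or late-dated event is certain.

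The window discussed is that of Groups 1 and 2. In Group 1 cohorts 1 to 3 the single-dose lead-in lengthens the window, but the gap after C1D22 is the same.

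**What to change.** 1. State in Section 3.2 that abnormalities first found on the C2D1 pre-dose safety samples count toward the DLT assessment.
2. Reconcile to that one endpoint the other wording in Section 3.2 (the 28-day DLT period and the MTD's first 28 days), Section 6.6 and Section 8.2.1.3. Changing the window sentence alone would leave new contradictions.
3. For subjects under DLT observation, draw those samples on Days 27 to 29, which Section 6.1.13 already permits for a nominal visit, instead of anywhere in ±7 days. With item 1 in place, a draw on Day 28 or 29 leaves no window day without a later qualifying count; a draw on Day 27 leaves one.
4. Require those results before the SRT decides.

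The samples are already collected, so no visit or test is added. The cost is a tighter booking for one visit, a wait of a few days at each cohort review, and possibly a slightly higher observed DLT rate.

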3.3. Study Treatments

Subjects who meet eligibility criteria will receive GS-5829 orally once daily. Subjects in the first 3 cohorts will receive a single dose of GS-5829 and then approximately 7 days later start their first 28 day cycle of GS-5829 once daily. Each cycle will consist of 28 days. Safety and efficacy assessments will occur on an outpatient basis including assessment of tumor response, physical exam, vitals, electrocardiogram (ECG), collection of blood samples (for routine safety labs, GS-5829 PK, CCI [REDACTED] at applicable visits), urine pregnancy (every 4 weeks while receiving GS-5829 in females of childbearing potential), and assessment of AEs. In addition, subjects will undergo computed tomography (CT)/magnetic resonance imaging (MRI) or applicable scans every 8 weeks for the first year and then every 12 weeks. Subjects in Group 3 will undergo a PET/CT if available instead of a CT scan alone at week 16.

A subject who does not show evidence of disease progression by clinical assessment or by CT/MRI or applicable scan may continue receiving GS-5829 once daily until disease progression (clinical or radiographic), unacceptable toxicity, withdrawal of consent, or other reasons specified in Section 3.4.

For subjects in Group 2, a radionuclide bone scan (whole body) is also required at screening and then as clinically indicated or to confirm a complete response.

Study drug dosing will continue in the absence of disease progression or toxicity warranting discontinuation of therapy.

3.4. Criteria for Discontinuation of Study Drug

Study medication may be discontinued in the following instances:

- Documented progression of malignant disease
- Pregnancy

- Investigator discretion
- Non-compliance with study drug
- Subject never dosed with study drug
- Protocol violation
- Subject decision
- Lost to follow-up
- Study termination by the sponsor
- Intercurrent illness that would, in the judgment of the investigator, affect assessments of clinical status to a significant degree
- Unacceptable toxicity, as defined in the toxicity management section of the protocol, or toxicity that, in the judgment of the investigator, compromises the ability to continue study-specific procedures or is considered to not be in the subject's best interest

3.5. Criteria for Removal from Study

Subjects may be removed from the study for the following reasons:

- Documented progression of malignant disease
- Death
- Pregnancy
- Investigator discretion
- Non-compliance with study drug
- Protocol violation
- Withdrawal of consent
- Lost to follow-up
- Study termination by the sponsor

4. SUBJECT POPULATION

4.1. Number of Subjects and Subject Selection

Up to 160 subjects who meet the eligibility criteria will be enrolled.

4.2. Inclusion Criteria

Subjects must meet all of the following inclusion criteria to be eligible for participation in this study.

- 1) Male or female ≥ 18 years of age. Subjects in Group 2 must be female.
- 2) Group 1: Histologically or cytologically confirmed advanced malignant solid tumor or lymphoma (any subtype) that is refractory to or intolerant of standard therapy or for which no standard therapy is available.
- 3) Group 2: Histologically or cytologically confirmed breast cancer with evidence of metastatic or locally advanced disease not amenable to resection or radiation therapy with curative intent and who have progressed during treatment with at least one prior hormonal therapy. Prior chemotherapy for advanced/metastatic disease is allowed.
 - a. Documentation of ER positive ($\geq 1\%$ positive stained cells by local standards) based on the most recent tumor biopsy, unless bone only disease.
 - b. HER2-negative tumor based on local testing on most recent tumor biopsy (immunohistochemistry score 0/1+ or negative by in situ hybridization HER2/CP17 ratio < 2 or for single probe assessment HER2 copy number < 4)
 - c. Post, pre or peri-menopausal subjects to be in the post-menopausal state as defined by one of the following:
 - i. Age ≥ 60 years
 - ii. Age < 60 years and cessation of regular menses for at least 12 consecutive months in the absence of chemotherapy, tamoxifen, toremifene, or ovarian suppression and serum estradiol and FSH level within the post-menopausal range
 - iii. Prior bilateral oophorectomy
 - iv. Pre/perimenopausal women can be enrolled if amenable to be treated with the LHRH agonist goserelin. Patients must have commenced treatment with goserelin or an alternative LHRH agonist at least 4 weeks prior to first dose of study drug. If patients have received an alternative LHRH agonist prior to study entry they must switch to goserelin for the duration of the study.

- 4) Group 3 lymphoma expansion: Subjects with lymphoma are limited to diffuse large B-cell lymphoma or peripheral T-cell lymphoma that are refractory to or intolerant of standard therapy or for which no standard therapy is available
- 5) All acute toxic effects of any prior antitumor therapy resolved to Grade ≤ 1 before the start of study drug dosing (with the exception of alopecia [Grade 1 or 2 permitted] and neurotoxicity [Grade 1 or 2 permitted])
- 6) ECOG Performance Status of ≤ 1
- 7) Life expectancy of > 3 months, in the opinion of the Investigator
- 8) Adequate organ function defined as follows:
 - a. Hematologic: Platelets $\geq 100 \times 10^9/L$; Hemoglobin ≥ 9.0 g/dL; ANC $\geq 1.5 \times 10^9/L$ (without platelet transfusion or any growth factors within previous 7 days of the hematologic laboratory values obtained at screening visit). Patients in the Group 3 lymphoma expansion may be enrolled with an ANC of $\geq 1.0 \times 10^9/L$; Platelets $\geq 75 \times 10^9/L$.
 - b. Hepatic: Aspartate transaminase (AST) / Alanine transaminase (ALT) ≤ 2.5 x upper limit of normal (ULN) (if liver metastases are present, ≤ 5 x ULN); Total or conjugated bilirubin ≤ 1.5 x ULN
 - c. Renal: Serum Creatinine ≤ 1.5 x ULN or creatinine clearance (CrCl) ≥ 60 ml/min as calculated by the Cockcroft-Gault method
- 9) Coagulation: International Normalized Ratio (INR) ≤ 1.2
- 10) Negative serum pregnancy test for female subjects ([Appendix 7](#))
- 11) Male subjects and female subjects of childbearing potential who engage in heterosexual intercourse must agree to use protocol specified method(s) of contraception as described in [Appendix 7](#).
- 12) Females who are nursing must agree to discontinue nursing before the first dose of GS-5829
- 13) Able and willing to provide written informed consent to participate in the study

